5.5.1.1.1 Severe allergic reactions (grade 3 or grade 4)

These require the immediate interruption of ABT-414 treatment and discontinuation from the study. Appropriate medical therapy including epinephrine, corticosteroids, intravenous antihistamines, bronchodilators, and oxygen should be available for use in the treatment of such reactions. Subjects should be carefully observed until the complete resolution of all signs and symptoms.

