5.5.4 Concomitant treatments

5.5.4.1 Prophylactic treatments

Anti-emetic prophylaxis should be given to lomustine treated patients on day 1 and to TMZ treated patients on day 1-3 or day 1-5 of every treatment cycle per local practice, and thereafter as clinically necessary. The use of 5HT-3 antagonists is recommended, and it is recognized they may cause constipation.

Hematopoietic growth factors: The prophylactic use of growth factors is not permitted during the screening period as a low hematologic lab value could be masked. Patients may receive red cell transfusions or erythropoietin to maintain hemoglobin > 9.9 mg/dL or 6.2 mmol/L.

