5.5.5 Other concomitant medication

Corticosteroids should be used in the smallest dose possible to control symptoms of cerebral edema and mass effect, and should be reduced and/or discontinued if possible.

No other anticancer agents or investigational drugs are allowed during the study or within 28 days before the inclusion into the trial, nor the participation into another study on investigational agents.

The use of live attenuated vaccines is prohibited during the study and for a period of 49 days after the end of ABT-414 administration.

The uses of concomitant medications that are contraindicated per the national prescribing information are prohibited during the conduct of the study

All concomitant medication will be collected on the CRFs.

6 Clinical evaluation, laboratory tests and follow-up

Patients with histologically confirmed glioblastoma may register and have their tumor tissue screened after diagnose and before tumor progression. Eligibility at the time of tumor progression will depend on the confirmation of EGFR amplification during the screening, the fulfillment of all other in- and exclusion criteria and the trial status (whether the study is still open for accrual).

Tumor tissue for EGFR assessment should be prepared and sent to central lab as described in the study specific study manual.

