6.3 From treatment start until end of protocol treatment

6.3.1 Day 1 of each cycle

All day 1 evaluations should be performed and laboratory results reviewed within 3 days before or at day 1 of the cycle, and prior to dosing. For day 1 of cycle 1, if the evaluations listed below have been already performed during the screening phase and within 2 weeks prior to this day 1, the same results can be used for cycle 1 and tests do not need to be repeated.

- Physical examination including, but not limited to, WHO performance status and neurological evaluation
- Ocular examination if clinically indicated (Arms 1 and 2 only)
- Hematology and biochemistry (as section 6.2)
- Vital signs (as section 6.2)
- Weight
- 12-lead ECG immediately after ABT-414 dosing on day 1 of cycle 1 and cycle 3, for subjects assigned to ABT-414 (Arm 1 or 2)
- Assessment of all adverse events according to CTCAE 4.0
- Concomitant medications, including steroid intake (maximal intake (mg per day)).

For patients in Arm 3A, lomustine, the above physical examination, hematology, vital signs and adverse event assessments need to be repeated at day 28 (+/- 3 days).

6.3.2 Day 1 and day 5 for cycles 1 and 2; day 1 for cycle 3 and every 2 cycles thereafter (day 1 of C5, C7 etc.)

- Pharmacogenetic (PG) sample: optional sample collection for all subjects that consent. If the PG sample is not collected at the Day 1 visit, it may be collected anytime during the study.
- For subjects assigned to ABT-414 (Arm 2) or ABT-414 in combination with TMZ (Arm 1): Pharmacokinetic (PK) and pharmacodynamic (PD) sample collection according to the following schedule. Refer to the study specific laboratory manual for detailed instructions on sample collection, volumes, processing and shipment.

	Cycle 1 Day 1 of ABT-414	Cycle 1 Day 5 (Day 4 up to day 7 is acceptable) of ABT-414	Cycle 2 Day 1 of ABT-414	Cycle 2 Day 5 (Day 4 up to day 7 is acceptable) of ABT-414	Cycle 3 Day 1 of ABT-414	Cycle 5, Cycle 7 etc. Every two cycles starting from ABT- 414 cycle 5	35 Day Safety Follow- up
PK – ABT-414, and Total ABT- 806 Assays	X ^a	X ^e	X ^a	X ^e	X ^a	X ^b	X ^c
PK - Cys- mcMMAF assay	X ^a	X ^e	X ^a	X ^e	X ^a	X ^b	
PK Antidrug Antibody Assay (ADA/nADA)	X ^b		X ^b		X ^b	X ^b	X ^c
PD Plasma Markers	X ^b		X ^b		X ^b		
PD serum markers	X ^b		X ^b		X ^b		
PG Sample (Optional)	X ^d						

- a. Samples will be collected before infusion (0 hour, pre-dose) and immediately after ABT-414 infusion

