7.1.1.4 Definition of response

For this trial, the primary measure of response and progression will be determined by central review according to the RANO criteria. All treatment decisions should be based on the RANO criteria as assessed by the local investigator. However, local investigators assessments will be confirmed by central radiographic review. The independent central radiologist will give feedback on investigator reads shortly after MRI submissions for the first 15 PFS events. In addition, top recruiting sites will receive more frequent feedback from the independent central radiologist. Otherwise, local MRIs will be assessed by central review in batches.

Although ORR, PFS endpoints will be mainly based upon central radiographic review, these endpoints based on investigator reviews will also be presented for comparisons.

Target lesions are measured in their two largest perpendicular diameters. Their area is conventionally calculated as the product of these diameters. In case of multifocal disease with more than one target lesion, the total tumor size is calculated as the sum of the area of all target lesions.

Response is defined as follows according to the RANO criteria, which also consider T2 weighted and FLAIR images:

- Complete response (CR) requires all of the following: 1) Complete disappearance of all enhancing measurable and non-measurable disease; 2) No new lesions; 3) Stable or improved non-enhancing abnormalities on FLAIR/T2 images as compared to baseline; 4) Patients must be off corticosteroids (or on physiologic replacement doses only) and stable or improved clinically.
- Partial response (PR) requires all of the following: 1) Only reductions of cross-sectional areas of 50% or more in the sum of product of perpendicular diameters of target lesions will be considered a response; when calculating the response, the baseline MRI must be used for comparison ; 2) No progression of non-target lesions; 3) No new lesions; 4) Stable or improved non-enhancing abnormalities on FLAIR/T2 images as compared to baseline; 5) Patients should be on a corticosteroid dose that should not be greater than the dose at time of baseline scan, and should be stable or improved clinically.

- Progressive disease (PD):

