The ORR will be compared between the treatment arms over the control arm using a one sided Cochran-Mantel-Haenszel (CMH) test, stratified by randomization stratification factors. Odds ratios will be presented with 95% CIs.

Best Overall Response Rate (BRR)

The number and percentage of subjects will be presented for each response category by treatment arm.

Complete Response Rate (CRR)

The same methodology as for analysis of objective response will be applied to complete response rate.

Corticosteroid Use

Systemic corticosteroids that were given orally or by injection, reported either in prior/concomitant medication form until 35 days after the last study drug (ABT-414/TMZ/lomustine) or tumor assessment form will be summarized. Baseline steroid use is defined as any use of systemic steroid prior to and within 14 days of randomization. Post-baseline steroid use is defined as any use of systemic steroid on or after randomization. Steroid dose will be converted to a dexamethasone equivalent dose.³

Table 3. Conversion Factor to Dexamethasone Equivalent Dose

Corticosteroids (mg)	Conversion Factor*
Cortisone	0.75/25
Hydrocortisone	0.75/20
Prednisone, Prednisolone	0.75/5
Methylprednisolone, Triamcinolone	0.75/4
Betamethasone	0.75/0.6

* Dexamethasone equivalent dose (mg) = Conversion factor x Corticosteroid dose (mg).

Baseline steroid dose is defined as the average dose prior to and within 14 days of randomization, i.e., sum of daily doses divided by the number of days treated with steroids. The following summary will be presented for each treatment arm:

- The number and percentage of subjects who are treated with steroids at baseline (yes; no; missing) and post-baseline (yes; no; missing) in a two-way table.
- For subjects with no steroids at baseline and at least one steroid at post-baseline, simple summary statistics for time (in weeks) to steroid use during the study since randomization.
- The number and percentage of subjects who are treated with average steroid dose group (mg/day) at baseline (≤ 2 ; > 2 to ≤ 4 ; > 4 to ≤ 6 ; > 6 to ≤ 8 ; > 8 to ≤ 20 ; > 20 mg/day).
- The number and percentage of subjects with objective response (CR and PR assessed by IRC per RANO criteria) and Kaplan-Meier estimates of PFS, by baseline steroid use status (yes; no; missing), respectively.

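### SAP 10.3 counts systemic steroids given for any reason as steroid use, so anti-emetic, anti-allergic and replacement doses could distort two of the steroid summaries between arms

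*SAP*

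**What the plan says.** SAP 10.3 (Corticosteroid Use) takes its data from "Systemic corticosteroids that were given orally or by injection, reported either in prior/concomitant medication form until 35 days after the last study drug", or from the tumour assessment form. The route restriction keeps out the steroid eye drops given with each ABT-414 infusion. Within what remains, "Baseline steroid use is defined as any use of systemic steroid prior to and within 14 days of randomization", and "Post-baseline steroid use is defined as any use of systemic steroid on or after randomization". Nothing restricts either definition by indication, dose or duration. Protocol 5.5.5 adds that "All concomitant medication will be collected on the CRFs", so a steroid given for any reason can reach the derivation.

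Three other sources of systemic steroid bear on this:

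- Anti-emetics, Protocol 5.5.4.1: "Anti-emetic prophylaxis should be given to lomustine treated patients on day 1 and to TMZ treated patients on day 1-3 or day 1-5" of every cycle. The choice is left to local practice and 5HT-3 antagonists are recommended. Nothing is scheduled for Arm 2.
- Allergic reactions to ABT-414, Protocol 5.5.1.1.1: "Appropriate medical therapy including epinephrine, corticosteroids, intravenous antihistamines, bronchodilators, and oxygen" are to be at hand. ABT-414 is given in Arms 1 and 2.
- Physiologic replacement, Protocol 7.1.1.4: for complete response, "Patients must be off corticosteroids (or on physiologic replacement doses only"). Replacement thus counts as off steroids there. SAP 10.3 has no such exemption.

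**The concern.** Steroid use is one of the outcomes named in the trial objectives (Protocol 2.1, SAP 4.1). Protocol 10.2 presents the need for steroids as information on clinical benefit, and Protocol 5.5.5 links corticosteroids to oedema and mass effect. A single anti-emetic or anti-allergic dose says nothing about that need, yet under SAP 10.3 it turns a non-user into a user and fixes the date of first use.

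The protocol separates such uses elsewhere. The complete-response rule sets replacement doses apart. The definition of clinical progression (Protocol 7.1.3.4) counts steroids started or raised for neurological signs and disregards short increases of a week or less. SAP 10.3 carries over neither distinction.

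The extra sources are also not spread evenly over the arms. At stake is whether a difference between arms in the yes/no table or in time to steroid use reflects the tumour or the supportive-care schedule.

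**Working it through.** The plan states no figure for steroid use, so there is nothing to reproduce. The check asks which of the outputs in SAP 10.3 could move, and by how much.

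**1. Which window is exposed.** Prior chemotherapy must have ended at least 4 weeks before randomization (Protocol 3.2), and the baseline window is 14 days. Anti-emetics for earlier chemotherapy should therefore not appear at baseline. Those given with study chemotherapy can appear after it.

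**2. Yes/no table, patients off steroids at baseline.** Let p be the share who start steroids for tumour symptoms, equal in both arms, and q the share of control patients given a steroid anti-emetic, independent of p. The documents give neither; the values below are assumptions. Users in Arm 3 = p + (1 − p)q, users in Arm 2 = p, and the spurious excess = q(1 − p).

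| p | q = 0 | q = 10% | q = 25% | q = 50% |
|---|---|---|---|---|
| 30%: Arm 3 v Arm 2 | 30 v 30 | 37 v 30 | 47.5 v 30 | 65 v 30 |
| excess (points) | 0 | 7 | 17.5 | 35 |
| 50%: Arm 3 v Arm 2 | 50 v 50 | 55 v 50 | 62.5 v 50 | 75 v 50 |
| excess (points) | 0 | 5 | 12.5 | 25 |

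Patients already on steroids at baseline cannot be reclassified. If s is their share, the whole-arm excess is (1 − s)q(1 − p), which is smaller.

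**3. Offset in Arm 2.** Let r be the share of Arm 2 given a steroid for an allergic reaction or for vomiting, which Protocol 5.5.1 lists as a potential ABT-414 toxicity. If q stands for all non-tumour steroid use in Arm 3, the net difference is (q − r)(1 − p). It shrinks as r rises and changes sign if r exceeds q. Arm 1 has both scheduled prophylaxis and ABT-414, so both sources act there.

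**4. Time to steroid use.** This is summarized only among patients off steroids at baseline who later use one. Treatment should start within 96 hours of randomization (Protocol 4), so an anti-emetic given on day 1 of cycle 1 sets the time within the first week. If all steroid anti-emetic use begins in cycle 1, the share of Arm 3 users with such an early time is at least q / [p + (1 − p)q]. With p = 30% and q = 25% this is 25/47.5 = 53%, enough to put the median there whatever the tumour-related need. With q = 10% it is 10/37 = 27%.

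**5. Reduction categories.** Sustained reduction needs at least a 50% lower dose for at least 50% of time on drug. Complete reduction needs discontinuation for at least 25% of that time. Days covered by scheduled prophylaxis:

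- TMZ, 3 days: 3/28 = 10.7%, so 89.3% off
- TMZ, 5 days: 5/28 = 17.9%, so 82.1% off
- Lomustine, 1 day: 1/42 = 2.4%, so 97.6% off

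A patient otherwise off steroids passes both thresholds in every case. Daily replacement is different: it leaves 0% of days off, below the 25% needed. Such a patient can satisfy the steroid condition for complete response and still fail complete reduction.

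**The case against.** The strongest case against the point is that its main mechanism is not in the documents. No section names a steroid as an anti-emetic, and Protocol 5.5.4.1 recommends another class. This stands: the anti-emetic part may be zero. A reader might infer that the tables will show a steroid-sparing effect of ABT-414 monotherapy over control. The documents do not support that, because q is unknown and anti-allergic or unscheduled anti-emetic steroids in Arm 2 work the other way.

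A reader might also infer that a one-day anti-emetic dose stands for a whole cycle in the reduction rules, because the cycle visit records "steroid intake (maximal intake (mg per day"). That is not supported either. SAP 10.3 names the medication and tumour assessment forms as its sources and builds the baseline dose from daily doses. No rule substitutes a cycle maximum.

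The consequences are small. Steroid use is exploratory, lies outside the testing sequence in SAP 4.6, and is summarized by arm without a test. An Arm 1 versus Arm 2 contrast is not among the planned comparisons. Protocol 8.2.1.2.2 does not confine the steroid analysis to the cited method, so a further summary is already permitted. All of this stands, and it limits the weight of the point.

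Finally, replacing the main definition by one based on indication could do harm. The trial is open label, indication is assigned by the investigator, and nausea and vomiting are also signs of raised intracranial pressure (Protocol 7.1.3.4). A filter could remove tumour-related use. This is a good reason to add a summary and not to replace the present one.

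**Conclusion.** The point holds in a limited form. The derivation has no filter on indication, dose or duration, and the non-tumour sources of systemic steroid are not scheduled alike across arms. The baseline by post-baseline table and the time to steroid use could therefore differ between arms for reasons unrelated to the tumour. Under the stated assumptions for p and q, the excess over Arm 2 ranges from 0 to 35 points among patients off steroids at baseline, before any offset in Arm 2; the net direction is unknown. The reduction categories are hardly affected by anti-emetic days. The handling of replacement doses in complete reduction is inconsistent with the complete-response rule whatever q is, though nothing shows that replacement differs by arm. OS, PFS, ORR and the alpha plan are untouched. This is a cheap improvement to an exploratory endpoint that is a named objective.

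**What to change.** In SAP 10.3, before database lock:

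1. Keep the any-use tables as they are.
2. Pre-specify a parallel summary of post-baseline steroid use and time to steroid use that leaves out records given for anti-emetic prophylaxis, allergic or infusion reaction, or physiologic replacement.
3. Classify records by recorded indication where there is one, and otherwise by review blinded to arm. Keep ambiguous records as tumour-related, which guards against deleting steroids given for raised intracranial pressure.
4. Treat physiologic replacement as off steroids for complete reduction, as Protocol 7.1.1.4 does for complete response.

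The cost is SAP wording, one more set of tables and some record review. The parallel summary relies on investigator-recorded indication in an open-label trial, and the documents do not show that indication is captured on either source form. If it is not, the review in step 3 carries most of the work. No change to sample size, alpha or treatment is needed.

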- For non-operated patients, recurrent disease must include at least one bi-dimensionally measurable contrast-enhancing lesion with clearly defined margins by MRI scan, with minimal diameters of 10 mm, visible on 2 or more axial slices 5 mm apart, based on an MRI scan done within 2 weeks prior to randomization
- Stable or decreasing dosage of steroids for 7 days prior to the baseline MRI scan
- No current or recent (within 4 weeks before randomization) treatment with another investigational drug
- Patients who require anti-convulsant therapy must be taking non-enzyme inducing antiepileptic drugs (non-EIAED). Patients previously on EIAED must be fully switched to non-EIAED at least 2 weeks prior to randomization
- No underlying or previous conditions that could interfere with treatment, including but not limited to:
 - no evidence of active infection requiring hospitalization or antibiotics, within 2 weeks prior to randomization
 - no active infectious keratitis
 - no other diseases interfering with follow up
- No planned vaccinations with live vaccines
- Adequate hematological function defined as: neutrophils $\geq 1.5 \times 10^9$ cells/L and platelets $\geq 100 \times 10^9$ cells/L and hemoglobin ≥ 6.2 mmol/L (9.9 g/dl)
- Normal liver function: bilirubin $< 1.5 \times$ upper limit of the normal range (ULN), alkaline phosphatase and transaminases (ASAT) $< 2.5 \times$ ULN
- Renal function: calculated creatinine clearance ≥ 30 mL/min by the Cockcroft-Gault formula (see [Appendix E](#))
- Absence of pregnancy. Women of childbearing potential (WOCBP) must be using an adequate method of contraception to avoid pregnancy throughout the study and for 6 months beyond the end of treatment in such a manner that the risk of pregnancy is minimized. In general, the decision for appropriate methods to prevent pregnancy should be determined by discussions between the investigator and the study subject. WOCBP include any female who has experienced menarche and

who has not undergone successful surgical sterilization (hysterectomy, bilateral tubal ligation, or bilateral oophorectomy) or is not postmenopausal. Females should not be breastfeeding.

- Post menopause is defined as: amenorrhea ≥ 12 consecutive months without another cause or for women with irregular menstrual periods and on hormone replacement therapy (HRT), a documented serum follicle stimulating hormone (FSH) level > 35 mIU/mL

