In addition, steroid dose change (sustained reduction and complete reduction) relative to baseline will be summarized. Sustained reduction of steroid dose is defined as 50% or more steroid dose reduction, relative to baseline, for 50% or more of the time on study drug (ABT-414/TMZ/lomustine). Complete reduction is defined as discontinuation of steroid use for $\geq 25\%$ of the time on study drug (ABT-414/TMZ/lomustine).

- The number and percentage of subjects with objective response status (responders; non-responders) and Kaplan-Meier estimates of PFS for subjects who have sustained steroid reduction and for subjects who have complete steroid reduction, respectively.

Quality of Life

Subject self-reported health related quality of life (HRQoL) outcomes are assessed at the baseline, Week 8 MRI visit (while on-treatment), Week 16 MRI visit (while on-treatment), and Month 6 visit (any time during the 6th and 7th month after the date of

randomization regardless of treatment or progression status) by using the QLQ-C30 version 3 (Table 4) and QLQ-BN20 (Table 5).

The main objective of HRQoL assessment is to determine the impact of ABT-414 on overall global health and HRQoL. A secondary objective is to evaluate the effect of the treatment on the remaining symptoms and functioning scales as treatment-related side effects may have a (temporary) negative influence on the health related domains of HRQoL of these subjects. The QLQ (quality of life questionnaire) comprises distinct scales, each of which represents a different aspect of QoL, and the individual questions on the QLQ are called items.

The QLQ-C30 is composed of global health status/QoL scale; five functional scales (physical, role, emotional, cognitive, and social); three symptom scales (fatigue, nausea and vomiting, and pain); and six single items (dyspnea, insomnia, appetite loss, constipation, diarrhea, and financial difficulties).

Table 4. Scoring the QLQ-C30

QLQ-C30	Item (Question) Numbers	Item Range*
Global health status/QoL		
Global health status/QoL	29, 30	6
Functional scales		
Physical functioning	1, 2, 3, 4, 5	3
Role functioning	6, 7	3
Emotional functioning	21, 22, 23, 24	3
Cognitive functioning	20, 25	3
Social functioning	26, 27	3
Symptom scales/Items		
Fatigue	10, 12, 18	3
Nausea and vomiting	14, 15	3
Pain	9, 19	3
Dyspnea	8	3
Insomnia	11	3
Appetite loss	13	3
Constipation	16	3
Diarrhea	17	3
Financial difficulties	28	

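### SAP 10.3 can record steroid 'reduction' on study for patients whose dose fell before randomization and has not changed since

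*SAP*

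**What the plan says.** The Corticosteroid Use part of SAP 10.3 sets its own baseline. "Baseline steroid use is defined as any use of systemic steroid prior to and within 14 days of randomization". "Baseline steroid dose is defined as the average dose prior to and within 14 days of randomization", which is spelled out as the "sum of daily doses divided by the number of days treated with steroids".

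It then announces that "steroid dose change (sustained reduction and complete reduction) relative to baseline will be summarized". Sustained reduction means "50% or more steroid dose reduction, relative to baseline, for 50% or more of the time on study drug". For the second category, "Complete reduction is defined as discontinuation of steroid use for" at least 25% of the time on study drug. The categories are used to tabulate objective response and to give "Kaplan-Meier estimates of PFS for subjects who have sustained steroid reduction", with the same for complete reducers. The baseline dose also feeds a table of dose groups from 2 mg/day or less to more than 20 mg/day.

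Three other places matter:
- SAP 6.0 gives a general baseline rule, the last available value up to and including randomization, which applies unless another is specified. SAP 10.3 specifies another.
- Protocol 3.2 requires "Stable or decreasing dosage of steroids for 7 days prior to the baseline MRI scan", so a falling dose before entry is allowed.
- Protocol 8.2.1.2.2 says steroid use will be analyzed with a cited published method, though not only with that.

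**The concern.** A reduction summarized over time on study drug should describe what happened to the dose on study drug. The SAP's rules look back 14 days, accept any use in that window, and never ask whether the patient was still taking steroids at randomization. A taper completed before the first dose of study drug can then be reported as a reduction on treatment.

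Steroid use compared with control is a named trial objective (Protocol 2.1, SAP 4.1). The groups of sustained and complete reducers are also used to describe response and PFS. If those groups mix patients whose dose fell on treatment with patients whose dose fell before it, neither the counts nor the response and PFS summaries can be read as intended.

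**Working it through.** The documents state no count, rate or power for this analysis, so there is no figure to reproduce. The check applies the SAP rules to invented dose histories: 14 days before randomization, then 56 days on study drug, in dexamethasone-equivalent mg/day. Three baselines are compared:
- SAP: sum of doses ÷ treated days.
- Calendar mean: sum of doses ÷ 14.
- Last dose: the dose on the last day up to randomization, zero if none was taken.

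Reduction = 1 − (dose on study ÷ baseline).

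| History before randomization | On study | SAP baseline | Calendar mean | Last dose |
|---|---|---|---|---|
| A. 8 mg for k days, then off | 0 mg | 8.0: 100% reduction; sustained and complete | 8k/14 = 0.57 (k=1), 2.86 (k=5), 4.0 (k=7), 7.43 (k=13): 100% reduction; sustained and complete | 0: not assessable |
| B. 8 mg for 4 days, then off | 3 mg | 8.0: 1 − 3/8 = 62.5%; sustained | 32/14 = 2.29: an increase; neither | 0: not assessable |
| C. 16 mg for 7 days, 4 mg for 7 days | 4 mg | 140/14 = 10.0: 1 − 4/10 = 60%; sustained | 10.0: 60%; sustained | 4: 0%; neither |
| D. 4 mg throughout | 4 mg | 4.0: 0%; neither | 4.0: 0%; neither | 4: 0%; neither |

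What the cases show:
1. In A and C the dose is the same at randomization and throughout the study, yet the SAP rule records sustained reduction. In A it also records complete reduction if discontinuation simply means being off steroids.
2. Replacing the treated-days denominator by 14 changes nothing in A or C. At 0 mg any positive baseline gives a 100% reduction, and the complete rule does not use the baseline dose. The cause is the any-use window together with the missing requirement of use at randomization.
3. The denominator does its own harm in B. A patient at 0 mg at randomization who later takes 3 mg/day is recorded as a 62.5% reducer.
4. The denominator also moves patients between baseline dose groups. One 8 mg day gives 8 mg/day (group >6 to ≤8) rather than 8/14 = 0.57 (≤2). A taper of 16, 16, 12, 12, 8, 8, 4, 4 mg followed by 6 days off gives 80/8 = 10 (>8 to ≤20) rather than 80/14 = 5.7 (>4 to ≤6).
5. The misclassification has limits. Take a patient with 8 mg for 5 days, off at randomization, who later restarts 8 mg. Off for 28 of 56 days (50%) meets both rules, 14 of 56 (25%) meets complete only, and 10 of 56 (18%) meets neither. A patient off for more than 14 days before randomization has no baseline dose and does not enter.

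**The case against.** The SAP's definition is open and reproducible, and a mean over treated days is a legitimate description of dose while on steroids. It may come from the published method that the protocol cites; that cannot be checked here, and departing from it could cost comparability. Complete reduction is introduced as a change relative to baseline, and discontinuation could mean stopping after study drug starts, which would keep patients already off steroids out of that category. The endpoint is exploratory, and SAP 10.3 specifies no between-arm test of these categories. All of this stands, and it limits the importance of the point. It does not rescue sustained reduction, which patients A and C meet on the words of the rule. For complete reduction, the doubt about what discontinuation means is itself something the SAP should settle.

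A reader might infer three stronger things that the documents do not support:
- *That the treated-days denominator causes patients already off steroids to be counted as reducers.* Case A shows that it does not.
- *That the problem is common.* Allowing a stable or decreasing dose before the MRI does not mean patients are off steroids at randomization. Re-operated patients must have had surgery at least 2 weeks before randomization, so only a taper running on into the window counts. No document gives the share affected.
- *That the rule favors ABT-414.* Tapering before randomization should balance across arms on average. If a share s of baseline users in each arm qualified this way, a between-arm difference would be multiplied by 1 − s, for example 0.9 at s = 10% and 0.7 at s = 30%. Both shares are assumptions, and the formula takes every such patient as qualifying. It describes dilution, not bias toward one arm.

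**Conclusion.** The definitional gap is real. As written, SAP 10.3 can class as sustained reducers patients whose dose has not changed since randomization, and as complete reducers those already off steroids if discontinuation is read plainly. The treated-days denominator is a separate and smaller fault: it raises baseline dose groups and can turn a later, lower non-zero dose into a false reduction.

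The consequence is inflated reduction counts and response and PFS summaries that mix two kinds of patient. How many patients are affected cannot be derived from the documents, and the dose histories above are illustrations only. No primary or secondary conclusion is affected. The change is worth making before database lock because the categories otherwise do not measure what their names say.

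**What to change.** In SAP 10.3, for the reduction analyses:
- Take the baseline dose as the last daily dexamethasone-equivalent dose on or before randomization, in line with the general rule in SAP 6.0. Say that a day without steroids counts as zero, so that the last recorded non-zero dose is not carried forward. SAP 10.3 currently counts the day of randomization as post-baseline, so state on which side that day falls.
- Assess sustained and complete reduction only in subjects on systemic steroids at that point.
- State that the reduction or discontinuation must start after randomization.

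For the dose-group table, count steroid-free days as zero in any averaged baseline dose.

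A shorter averaging window alone would not be enough. Over the last 7 days, 16, 12, 12, 8, 8, 4, 4 mg averages 64/7 = 9.14 mg/day, so a patient who simply stays on 4 mg would still show 1 − 4/9.14 = 56% and be counted as sustained.

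The cost is a few lines of SAP text using the same steroid records. Fewer patients will be assessable for reduction, and comparability with the cited published method may suffer. The current definitions can be kept as a supplementary summary for that purpose.
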